### 15.4 Analysis of Secondary Endpoints

Constipation is defined as <3 bowel movements in the past week and/or Bristol Stool type 1 or 2. The secondary endpoint upon which the sample size is based is the number (%) of enrolled subjects with any occurrence of constipation during 1 month of follow-up (the period prevalence). Treatment for GI symptoms and constipation will be summarized based on the percentage of enrolled subjects receiving and initiating treatment at time of enrollment visit. To evaluate whether CF subjects are adequately treated, the number and percentage of subjects with GI symptoms and constipation on treatment will be reported. All GI related treatments will be classified by medication type/class.

Individual GI symptoms will be extracted from the PAC-SYM and PAGI-SYM questionnaires. For each GI symptom, frequency and severity will be summarized at each assessment as follows: number (%) of subjects with GI symptom, severity of GI symptom (mean score and distribution of severity score) and change in severity scores from the enrollment visit by whether subjects were receiving treatment.

Mean overall (and by sub-scale) PRO scores for PAC-SYM, PAGI-SYM and PAC-QOL at scheduled assessments will be reported including evaluation of within and between subject variability. Group comparisons of mean scores by subjects receiving/not receiving treatment and by those with/without constipation will also be made. Absolute change in PRO scores from enrollment visit to scheduled assessments will be reported based on subjects receiving/not receiving treatment for constipation. To examine these effects, figures displaying mean PRO scores by scheduled assessment will be created. Additionally, mixed effects models for repeated measures will be fit with PRO scores as the outcome and covariates for visit, treatment, pancreatic status, age group and the interaction between treatment and visit.

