2.3 Definition of the Analysis Populations

Enrollment:

An enrolled participant was defined as a participant who had met all eligibility criteria, and fully completed (i.e. no question left unanswered) at least one of the ePRO questionnaires (PAC-SYM, PAGI-SYM, PAC-QOL, and disease-specific) at baseline.

Baseline:

Baseline refers to the enrollment visit of enrolled participants, at which informed consent was given, eligibility was met, and medical history was collected.

Follow-up weeks:

GALAXY Statistical Analysis Plan 12/16/2019 - CONFIDENTIAL

Follow-up occurred at week 1 (day 7, +1), week 2 (day 14, +1), and week 4, (day 28, +1). These were outside-of-clinic, i.e. participants are asked to complete the ePRO via their mobile devices. The questionnaires took approximately 10 minutes to complete. For participants \geq 2 years of age to $<$ 12 years of age, the parent/guardian completed the questionnaire. For participants \geq 12 years of age, the participant completed the questionnaire.

Protocol-defined constipation:

Per protocol, constipation is defined as $<$ 3 bowel movements in the past week and/or Bristol Stool type 1 or 2.

3. Overview of Planned Analyses

Unless otherwise noted, the endpoints of this study are mostly descriptive, with all continuous outcomes such as symptom severity and PRO scores evaluated using descriptive statistics such as mean, median, standard deviation, and 95% confidence intervals. Presence/absence of symptoms will be shown as percentages and corresponding 95% confidence intervals calculated using the Wilson method. Longitudinal models will be mixed-effect models with participant-specific random effect and compound symmetry covariance structure. Except where otherwise noted, all tests will be two-sided and statistical significance will be determined at the 0.05 level. No adjustment for multiple comparisons will be made.

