3.4 Secondary Endpoints

3.4.1 The feasibility of ePRO surveys conducted outside-the-clinic setting:

1. At each scheduled outside-the-clinic assessment, number (%) of participants with at least one PRO fully completed
2. For each PRO, number (%) of participants with fully completed questionnaires at each scheduled outside-the-clinic assessment and overall
3. Number (%) of completed PROs by age and site

The corresponding analyses are outlined in Appendix A, Section A.3.

3.4.2 Prevalence and variability of GI symptoms:

Evaluation of PRO scores overall and by sub-scale at scheduled assessments:

4. Mean PRO score for PAC-SYM, PAGI-SYM, and PAC-QOL
5. Within- and across-participant variability of PRO scores

Descriptive statistics will be used to visually summarize the total scores and domain scores over time, and by age group. Longitudinal summaries will be provided, using mixed-effect models with participant-specific random intercepts. The corresponding analyses are outlined in Appendix A, Section A.4.

Evaluation of the prevalence of protocol-defined constipation:

6. Number (%) of enrolled participants with any occurrence of protocol-defined constipation during 1 month of follow-up (the period prevalence)

Descriptive statistics will be used to summarize the protocol-defined constipation, as well as other information from the disease-specific questionnaire over time, and by age group. The corresponding analyses are outlined in Appendix A, Section A.5.

Evaluation of the frequency and severity of each GI symptom at scheduled assessments and overall:

7. Number (%) of participants with presence of GI symptom
8. Distribution of severity scores of GI symptom
9. Mean severity score of GI symptom
10. Mean severity score of GI symptom
11. Distribution of stool frequency and type by Bristol Stool Scale

12. Change in distribution of GI symptoms and stool frequency/type from baseline visit overall

Pre-specified GI symptoms of interest, i.e. particular questions from the ePROs, are identified. Descriptive statistics will then be used to summarize the distributions of these GI symptoms overall, by age group, and the change from baseline. The corresponding analyses are outlined in Appendix A, Section A.5.

Evaluation of PAC-SYM, PAGI-SYM, and PAC-QOL scores by protocol-defined constipation:

13. Mean total and domain scores (also mean difference and 95% confidence interval) comparing participants with and without protocol-defined constipation

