Descriptive statistics will be used to summarize the total and domain scores by protocol-defined constipation. Longitudinal summaries will be provided, using mixed-effect models with participant-specific random intercepts, as well as fixed effects for weekly protocol-defined constipation status, visit, and age group. The predictor of interest is the protocol-defined constipation status. The corresponding analyses are outlined in Appendix A, Section A.5.

Evaluation of alternative CF-specific definitions of constipation:

14. Examine alternative definitions of constipation that are CF specific based on correlation with PRO questionnaires and maximizing the area under the receiver operating characteristic (ROC) curve for PAC-SYM scores
15. Number (%) reporting constipation based on patient self-assessment. Examine concordance of self-reported constipation against protocol/alternate definitions using Cohen's kappa coefficient

The corresponding analyses are outlined in Appendix A, Section A.6.

3.4.3 Current management of GI symptoms:

16. Number (%) of all participants receiving treatment at baseline
17. Number (%) of all participants initiating treatment at baseline
18. Number (%) of all participants receiving treatment by medication class/type
19. Among participants with GI symptoms and constipation, number (%) receiving treatment
20. Change in distribution of GI symptoms and stool frequency/type by GI treatment at baseline
21. Mean PRO scores (also mean differences and 95% confidence interval) by GI treatment at baseline
22. Among participants receiving or initiating treatment for constipation, mean absolute change in PRO scores over time overall and by medication type/class

The corresponding analyses are outlined in Appendix A, Section A.7.

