Exhibit 4.2 Distributions of Total Scores for PAC-SYM, PAGI-SYM, and PAC-QOL by Age

This figure summarizes the total scores for PAC-SYM, PAGI-SYM, and PAC-QOL at each week and overall, by age group.

[figure not shown]
[figure not shown]

Exhibit 4.3.x Distributions of [ePRO] Domain Scores by Week

This figure summarizes the distributions of domain scores for [ePRO] by week.

[figure not shown]

Exhibit 4.3.1 Distributions of PAC-SYM Domain Scores by Week
Exhibit 4.3.2 Distributions of PAGI-SYM Domain Scores by Week
Exhibit 4.3.3 Distributions of PAC-QOL Domain Scores by Week

Note:

- PAC-SYM and PAC-QOL are 5-point scale while PAGI-SYM is 6-point scale
- PAC-SYM has 3 domains, PAGI-SYM has 6 domains, and PAC-QOL has 4 domains

Exhibit 4.4.x Distributions of [ePRO] Domain Scores by Age Group

This figure summarizes the domain scores for [ePRO] at baseline and follow-up weeks by age group.

Exhibit 4.4.1 Distributions of PAC-SYM Domain Scores by Week and Age Group
Exhibit 4.4.2 Distributions of PAGI-SYM Domain Scores by Week and Age Group
Exhibit 4.4.3 Distributions of PAC-QOL Domain Scores by Week and Age Group

Note:

- PAC-SYM and PAC-QOL are 5-point scale while PAGI-SYM is 6-point scale
- PAC-SYM has 3 domains, PAGI-SYM has 6 domains, and PAC-QOL has 4 domains

Exhibit 4.5.1 Model-based Summary of PAC-SYM, PAGI-SYM, and PAC-QOL Total and Domain Scores

This figure provides model-based summaries of the total and domain scores, for all participants and subgroups stratified by age. The estimates are obtained from mixed-effect models with participant-specific random intercepts.

[figure not shown]

Exhibit 4.5.2 Comprehensive Model-based Summary of PAC-SYM, PAGI-SYM, and PAC-QOL Total and Domain Scores

This table is an extended version of Exhibit 4.5.1 with further details on the model-based summaries of the total and domain scores, for all participants and subgroups stratified by age, including the within-subject and between-subject variance estimates. The estimates are obtained from mixed-effect models with participant-specific random intercepts.

	Age <18 Years (N=n)			Age ≥18 Years (N=n)			All Participants (N=n)		
	Mean (95% CI)	Within- Subject Variance	Between -Subject Variance	Mean (95% CI)	Within- Subject Variance	Between -Subject Variance	Mean (95% CI)	Within- Subject Variance	Between -Subject Variance
PAC-SYM Total Score (NN=nn)									
Abdominal Symptoms (NN=nn)	x.X (x.x, x.x)	x.xx	x.xx						
Rectal Symptoms (NN=nn)									

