The following table shows the changes in GI symptoms from baseline at each follow-up week. This is a collapsed version with less details compared to the 5.4.x exhibits.

GI Symptom	Baseline Mean (95% CI)	Week 1					Week 2					Week 4				
		N [1]	Mean (95% CI)	Worsen – n (%)	No Change – n (%)	Improved – n (%)	N [1]	Mean (95% CI)	Worsen – n (%)	No Change – n (%)	Improved – n (%)	N [1]	Mean (95% CI)	Worsen – n (%)	No Change – n (%)	Improved – n (%)
Symptom 1	Mean (95% CI)	n	mean (CI)	n (%)	n (%)	n (%)	n	mean (CI)	n (%)	n (%)	n (%)	n	mean (CI)	n (%)	n (%)	n (%)
Symptom 2																
...																
Symptom s																

[1] N per each follow-up week is defined as the number of participants who had data at both baseline and the follow-up week.

Exhibit 5.5.1 Summary of PAC-SYM, PAGI-SYM, and PAC-QOL Total Score by Protocol-Defined Constipation

This figure summarizes the distribution of total scores for PAC-SYM, PAGI-SYM, and PAC-QOL by **weekly** protocol-defined constipation status

[figure not shown]
[figure not shown]

Exhibit 5.5.2 Summary of PAC-SYM, PAGI-SYM, and PAC-QOL Total Score by Self-Defined Constipation

Similar figure to Exhibit 5.5.1 but using self-defined constipation.

Exhibit 5.6.1 Model-based Summary of PAC-SYM, PAGI-SYM, and PAC-QOL Total and Domain Scores by Protocol-Defined Constipation

This figure provides model-based summaries of the total and domain scores, for all participants and by weekly protocol-defined constipation. The estimates are obtained from mixed-effect models with participant-specific random intercepts, as well as fixed effects for protocol-defined (weekly) constipation status, week, and age group. The predictor of interest is constipation status.

Exhibit 5.6.2 Model-based Summary of PAC-SYM, PAGI-SYM, and PAC-QOL Total and Domain Scores by Self-Defined Constipation

Similar figure to Exhibit 5.6.1 but using self-defined constipation.

A.6 Summary of Alternative CF-Specific Definitions of Constipation

Exhibit 6.1.x Summary of PAC-SYM total score by constipation status defined by [protocol or specific rules]

This figure (one figure per one definition of constipation) shows how the distribution of PAC-SYM total score looks with different definition for constipation, and an in-sample ROC curve constructed by using PAC-SYM total score in a longitudinal model as a classifier for the corresponding weekly constipation status.

[figure not shown]

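### SAP Exhibit 4.5 specifies its variance-component models without a visit term, so any common shift between the enrollment visit and the home assessments would be counted as within-subject variability

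*SAP*

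**What the plan says.** SAP section 3.4.2 lists as an endpoint "Within- and across-participant variability of PRO scores". For its analysis the SAP says "Longitudinal summaries will be provided, using mixed-effect models with participant-specific random intercepts" and names no other term. Exhibits 4.5.1 and 4.5.2 repeat this: "The estimates are obtained from mixed-effect models with participant-specific random intercepts". Exhibit 4.5.2 is the table that reports the scores "including the within-subject and between-subject variance estimates". Its shell has one mean with a confidence interval and two variances per score and age column, with no mean by week.

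The general rule in SAP section 3 is "Longitudinal models will be mixed-effect models with participant-specific random effect and compound symmetry covariance structure". It sets the covariance structure and gives no default visit effect.

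Elsewhere the SAP names the time term. The constipation model in section 3.4.2 has random intercepts "as well as fixed effects for weekly protocol-defined constipation status, visit, and age group". Exhibit 5.6.1 has them "as well as fixed effects for protocol-defined (weekly) constipation status, week, and age group". Exhibit 7.4, the treatment model, also lists week.

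By the schedule of events, PAC-SYM and PAGI-SYM are completed once at the enrollment visit and three times outside the clinic (Days 7, 14 and 28). PAC-QOL is completed once at enrollment and once outside the clinic (Day 28).

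**The concern.** A random-intercept model with a single overall mean splits variation into two parts: differences between people, and everything else. If scores move together between the enrollment visit and the later assessments, that common movement falls into the second part and is reported as within-subject variance. It is a mean effect, not scatter within a person.

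Some common movement is plausible. The setting changes from clinic to home, SAP section 3.4.3 allows for participants initiating treatment at baseline, and the SAP plans to report change from baseline.

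Variability is a named endpoint, and Protocol 15.7 counts its estimation among the things that 400 subjects allow. The protocol also means the study to inform later algorithm-based work. If a later study is sized on change from baseline, the variance of a change is twice the within-subject variance, so the required sample size rises in the same proportion as any inflation.

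**Working it through.** **1. The plan's own figure.** Protocol 15.7 gives a 95% interval of 0.44 to 0.63 (width 0.19) for a variance of 0.52 in 240 adults. The chi-square interval (n−1)s²/χ² with n = 240 and s² = 0.52 gives 0.438 to 0.627, width 0.189. It reproduces.

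**2. Effect of a common shift.** Let scores at one of m assessments differ by d from the rest, in everyone, with complete data.

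- Within-subject: the visit means (0, −d, −d, −d) have sum of squares d²(m−1)/m. Dividing by m−1 gives an addition of d²/m: d²/4 for m = 4 and d²/2 for m = 2.
- Between-subject: this is estimated by (MS between − MS within)/m. The shift leaves MS between unchanged and raises MS within by d²/m, so the estimate falls by d²/m²: d²/16 for m = 4 and d²/4 for m = 2.

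| d (points) | m = 4: within | m = 4: between | m = 2: within | m = 2: between |
|---|---|---|---|---|
| 0.1 | +0.0025 | −0.0006 | +0.005 | −0.0025 |
| 0.2 | +0.010 | −0.0025 | +0.020 | −0.010 |
| 0.3 | +0.0225 | −0.0056 | +0.045 | −0.0225 |

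**3. Check by simulation.** Mixed models were fitted by REML to 20 simulated data sets per setting, each with 400 subjects, between-subject variance 0.52, an assumed within-subject variance of 0.20 and no missing data. A shift of 0.5 was used only to make the effect easy to see.

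- m = 4: within-subject variance 0.265 without a visit factor and 0.201 with it (formula without it: 0.20 + 0.0625 = 0.2625).
- m = 2: 0.332 without and 0.202 with it (formula without it: 0.325).
- Between-subject variance without and with the factor: 0.503 and 0.518 for m = 4; 0.459 and 0.524 for m = 2.

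**4. Relative size.** The documents give no within-subject variance, so I assume a within-person correlation ρ of 0.6 to 0.8. The 0.52 can be read in two ways. Protocol 15.7 cites it as a baseline variance from adult chronic-constipation trials, which suggests total variance at one time point, and then uses it as between-subject variance.

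- Total: 0.52(1−ρ) = 0.104 to 0.208.
- Between-subject: 0.52(1−ρ)/ρ = 0.13 to 0.347.

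| Shift 0.2 to 0.3 | 0.52 as total | 0.52 as between-subject |
|---|---|---|
| Four visits | 0.010/0.208 = 5% to 0.0225/0.104 = 22% | 0.010/0.347 = 3% to 0.0225/0.13 = 17% |
| PAC-QOL, borrowing 0.52 | 0.020/0.208 = 10% to 0.045/0.104 = 43% | 0.020/0.347 = 6% to 0.045/0.13 = 35% |

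At a shift of 0.1 the figures are about 1–2% for four visits and 1–5% for PAC-QOL.

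**5. Against sampling error.** With 400 complete participants and normal errors, the 95% sampling error of the within-subject variance is about ±1.96√(2/1200) = ±8% for four visits and ±1.96√(2/400) = ±14% for two. The bias can therefore be smaller or larger than the sampling error, depending on the shift. The between-subject effect is small: at 0.3 points it is 0.0056/0.52 = 1% or 0.0225/0.52 = 4%.

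**6. The single mean.** Suppose 12% of home assessments are missing, borrowing the planning rate in Protocol 15.7. With assessments weighted equally, the clinic share rises from 0.25 to 1/(1 + 3×0.88) = 0.275 for four visits, and from 0.50 to 1/1.88 = 0.532 for PAC-QOL. A shift of 0.3 then moves the mean by about 0.007 or 0.010 points. In the extreme case where the whole 12% leave after enrollment and each person counts equally, the four-visit share is 0.88×0.25 + 0.12 = 0.34, and the move is 0.09×0.3 = 0.027.

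**The case against.** **Silence is not exclusion.** No sentence says that visit is left out. The SAP is also not uniformly explicit: Exhibits 5.3.1 and 6.1 refer to a longitudinal model without listing its terms. This stands as a caution. But the Exhibit 4.5 model is described three times in the same way, and the shell with one mean per column fits an intercept-only model. A programmer following the text would omit visit.

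**A reader might infer that the SAP dropped a term promised in the protocol.** The documents do not support that. The model in Protocol 15.4 with "covariates for visit, treatment, pancreatic status, age group and the interaction between treatment and visit" is set out for the treatment comparison. Its SAP counterpart is Exhibit 7.4, which does include week.

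**A reader might infer that staff help at enrollment distorts the baseline answers.** Protocol 10.1 has staff assist with installing and registering the application and go over the instructions. The subject or parent/guardian then completes the questionnaires. Application and respondent rule are the same at home; the setting differs. Nothing in the documents shows that a shift occurs.

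**Total variability around a person's own mean is a legitimate quantity.** This is true, and the plan does not say which it wants. Exhibits 4.1 to 4.4 would also make a shift visible, although they would not take it out of the variance estimates. What stands is that the quantity should be stated, and that a variance net of visit means is the more useful planning input.

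**Conclusion.** The point holds as a minor, nearly free improvement. As written, the Exhibit 4.5 models would absorb any common shift between the enrollment visit and later assessments into the within-subject variance and slightly understate the between-subject variance.

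The algebra is exact for complete data, but the size in this study is unknown. The percentages depend on assumed shifts, an assumed correlation and the reading of 0.52. Those for PAC-QOL depend further on a variance for another instrument, taken from adults in chronic-constipation trials. They show what is possible and are not a forecast.

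A reader might also infer that drop-out seriously distorts the single reported mean. At 12% missing the effect is about 0.01 points with assessments weighted equally, and under 0.03 in the extreme case, so it adds little. The primary endpoint, the constipation prevalence and the sample size do not use these models and are unaffected.

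**What to change.** In SAP section 3.4.2 and Exhibits 4.5.1 and 4.5.2, specify visit as a categorical fixed effect alongside the participant random intercept, in each age column and overall. Report both variance components from that model, report the mean averaged equally over visits, and state that within-subject variance is net of visit means.

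The cost is one model term (three degrees of freedom for PAC-SYM and PAGI-SYM, one for PAC-QOL) and a sentence of text. No extra data are needed. The small downside is that the reported variance no longer includes systematic change between visits, which Exhibits 4.1 to 4.4 still show.
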